4. PLANNED ANALYSES

The following analyses will be performed for this study:

- Final Analysis

4.1. Final Analysis

All final, planned analyses identified in this SAP will be performed by IQVIA Biostatistics following Sponsor Authorization of this Statistical Analysis Plan, Database Lock, Sponsor Authorization of Analysis Populations.

5. ANALYSIS POPULATION

Agreement and authorization of patients included/excluded from each analysis population will be conducted prior to the database lock of the study.

5.1. Enrolled [ENR] Population

The Enrolled (ENR) population will contain all patients who are enrolled into the study (i.e. signed ICF and met the eligibility criteria) and may or may not receive the study medication (i.e., monotherapy and/or combination therapy). An enrolled patient who does not meet the inclusion/exclusion criteria might be included in the ENR population as per the investigator discretion.

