5.2. Modified Intent-to-Treat (mITT) Population

The Modified Intent-to-Treat (mITT) population will contain all patients who are in the Enrolled population, receive at least one dose of combination therapy, and have at least baseline and Week 8 assessments with primary efficacy data.

Document: \\eedc-vnasc01\Biosdata\Menarini\NebAml\ZZA67778\Biostatistics\Documentation\SAP\SAP_Menarini_MEIN21AmNe-Hyp001_Final_V1.0

Author: [name]

Version Number:

Final V1.0

Version Date:

11Nov2022

Template No.: CS_TP_BS016 Revision 7

Reference: CS_WI_BS005

Effective Date: 01Nov2021

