5.3. Safety (SAF) Population

The Safety population will contain all patients who are in the Enrolled population and receive at least one dose of study medication (i.e., monotherapy and/or combination therapy).

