5.4. Per-Protocol (PP) Population

The Per-Protocol (PP) population will contain all patients included in the Safety population who do not have any major protocol deviations that could affect the primary efficacy analyses and have at least baseline (Week 0) and Week 8 assessments with primary efficacy data.

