18. SAFETY OUTCOMES

All outputs for safety outcomes will be based on the SAF population.

There will be no statistical comparisons between the treatment groups for safety data, unless otherwise specified with the relevant section.

Document: \\needc-vnasc01\Biosdata\Menarini\NebAm\ZZA67778\Biostatistics\Documentation\SAP\SAP_Menarini_MEIN21AmNe-Hyp001_Final_V1.0

Author: [name]

Version Number:

Final V1.0

Version Date:

11Nov2022

Template No.: CS_TP_BS016 Revision 7

Reference: CS_WI_BS005

Effective Date: 01Nov2021

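### Safety membership depends on eligibility, with ineligible patients admitted only at investigator discretion, so dosed patients can be missing from every safety output

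*SAP*

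**What the plan says.** SAP 5.1 defines the Enrolled (ENR) set as patients who "signed ICF and met the eligibility criteria". It then adds: "An enrolled patient who does not meet the inclusion/exclusion criteria might be included in the ENR population as per the investigator discretion". No criterion, deadline or documentation is attached to that decision. SAP 3.3 lists the sentence among the changes from the protocol.

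The other sets are built on ENR:

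- Safety (SAP 5.3): "all patients who are in the Enrolled population and receive at least one dose of study medication", where study medication means monotherapy, combination therapy or both.
- mITT (SAP 5.2): "all patients who are in the Enrolled population, receive at least one dose of combination therapy", with baseline and Week 8 primary efficacy data.
- PP (SAP 5.4): "all patients included in the Safety population who do not have any major protocol deviations", again with baseline and Week 8 data.

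SAP 18 states: "All outputs for safety outcomes will be based on the SAF population". Protocol 12.3 has the same structure without the discretion sentence: Enrolled requires eligibility, and both Safety and mITT require Enrolled.

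On timing, SAP 5 says: "Agreement and authorization of patients included/excluded from each analysis population will be conducted prior to the database lock of the study". SAP 4.1 adds that the sponsor authorises the populations before the final analysis.

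**The concern.** A safety population should count everyone exposed. Here exposure is not enough: the patient must also have met eligibility or have been let in by the investigator. Patients who are dosed and then found ineligible are foreseen, because protocol 10 lists an exclusion criterion that had gone unrecognised at entry as a reason for withdrawal. Some may be at raised risk of an adverse event, since the exclusion criteria cover conditions such as severe renal impairment and clinically relevant hepatic impairment.

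At stake is the completeness of the adverse-event numerators and denominators. There is a smaller risk that membership of the primary analysis set is settled case by case by people who can see individual blood pressures.

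**Working it through.** **1. Trace one patient through the definitions.** Take a patient who signed consent, took study drug and was afterwards found not to have met a criterion.

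| Set | Condition | Not admitted by the investigator | Admitted |
|---|---|---|---|
| ENR (SAP 5.1) | met eligibility, or discretion | out | in |
| Safety (SAP 5.3) | ENR and one dose | out | in |
| mITT (SAP 5.2) | ENR, one combination dose, baseline and Week 8 data | out | in, if data exist |
| PP (SAP 5.4) | Safety, no major deviation, baseline and Week 8 data | out | depends on how the deviation is classed |

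Under protocol 12.3 read literally, only the third column applies: every such patient is out. The SAP sentence moves some to the fourth column, by choice.

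**2. Would the omission show?** SAP 9.1 presents disposition for all patients, but tabulates population sizes and reasons for exclusion for ENR only. A patient left out of ENR is not in that table. Under SAP 18 the safety listings use the Safety set too, so the patient is absent from them as well.

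**3. The plan's own figure.** The point does not depend on the sample size, but 216 is used below. With an assumed change of 4 mmHg, a null of 2 mmHg and SD 10 (protocol 12.2), the normal formula at one-sided 5% and 90% power gives n = (10 × (1.645 + 1.282) / 2)², which rounds up to 215. The exact t calculation gives 216, with power 0.901. (At the SAP's default two-sided 5%, power at 216 is 0.833; that is a separate matter.)

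**4. Number of patients.** None is given. Assumption: 3-5% of 216. 0.03 × 216 = 6.5 and 0.05 × 216 = 10.8, so about 6 to 11.

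**5. Effect on an adverse-event incidence.** Let N be the number dosed, e the number with the event and k the number left out. The reported incidence lies between (e − min(e, k)) / (N − k), if as many as possible of those left out had the event, and e / (N − k), if none did. The number dosed is not stated. I use 220 (two caps of 110 at Visit 2) and 290 (planned screened, a ceiling). The event counts of 5 and 20 are illustrative.

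| N | e | All dosed | k = 6 | k = 11 |
|---|---|---|---|---|
| 220 | 5 | 2.27% | 0.00% to 2.34% | 0.00% to 2.39% |
| 220 | 20 | 9.09% | 6.54% to 9.35% | 4.31% to 9.57% |
| 290 | 5 | 1.72% | 0.00% to 1.76% | 0.00% to 1.79% |
| 290 | 20 | 6.90% | 4.93% to 7.04% | 3.23% to 7.17% |

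Example: N = 220, e = 20, k = 11 gives (20 − 11)/(220 − 11) = 9/209 = 4.31%. The lower ends are extremes, not expectations.

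**6. Effect on the primary result.** On the basis in step 3, losing 3, 6 or 15 of 216 from mITT lowers power from 0.901 to 0.897, 0.893 or 0.881. If those left out differ in mean change from those kept by D, the mean shifts by (k/216) × D. With D = 10 mmHg, one SD and deliberately large, the shift is 6/216 × 10 = 0.28 or 11/216 × 10 = 0.51 mmHg. The planned standard error is 10/√216 = 0.68.

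**The case against.** The strongest reply is that the SAP sentence is more inclusive than the protocol, not less. That is right. A reader might infer that the SAP broke a sound definition; the documents do not support this, because protocol 12.3 already makes Enrolled depend on eligibility and nests Safety in it. Deleting the sentence alone would restore the stricter exclusion.

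A reader might also infer that patients can be removed once results are known. The documents do not show this either. Membership is settled before lock, deviations are reviewed case by case before lock (SAP 9.2), the sponsor must authorise the populations, and protocol 12.5.7 plans no interim analysis. The investigator is not the sole decider. The sentence can even be read as simply keeping a patient whom the investigator has already entered. What remains is narrower: none of these steps obliges anyone to put every dosed patient in Safety, and with open-label treatment individual outcomes are visible to those who decide.

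Third, a reader might conclude that run-in drug is given before laboratory results are known. Protocol 5.1 has screening procedures completed on the same day before run-in, laboratory testing is local, and no turnaround time is stated. Late results are a possible inference only. The withdrawal reason in protocol 10 is the firmer support.

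Finally, exposed patients do not vanish from the record. Adverse events are collected from consent (protocol 9.9), and all consenting patients are accounted for (SAP 9). That stands, but it does not replace tables on the exposed population.

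**Conclusion.** The defect is real and follows from the definitions alone: read together, protocol 12.3 and SAP 5.1 and 5.3 allow a dosed patient to be absent from all safety outputs, and the only exception has no criterion.

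Its size is not fixed by the documents. Six to 11 patients rests on an assumed 3-5% of 216; applying that rate to 290 would overstate it, because 290 includes screen failures who may never be dosed. At these numbers a common event is moderately distorted at worst, while an uncommon one could disappear from the tables.

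A claim that the primary mean change is materially biased is not supported. mITT also needs Week 8 data, which patients withdrawn for ineligibility may lack (although protocol 10 asks them to complete the Visit 4 assessments), and even the deliberately large shift above is below one standard error. Absence from PP is no fault in itself where ineligibility is a major deviation. The case rests on safety completeness and on having a fixed rule.

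**What to change.** 1. In SAP 5.3 and protocol 12.3, define Safety as all patients who received at least one dose of monotherapy or combination therapy, regardless of eligibility and independent of ENR.
2. In SAP 3.3 and 5.1, replace the discretion sentence with a fixed rule that keeps patients later found ineligible in ENR, and in mITT if they meet its dosing and data conditions.
3. Treat ineligibility only as a protocol deviation, acting through the PP set.

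This is a change of wording and needs no new data collection. The cost is small but not nil: the new definitions must be logged in SAP 3.3 and aligned with protocol 12.3, so that the two documents do not conflict. The sponsor should also check whether the mITT wording counts as a change to the primary analysis, which protocol 12.7 makes subject to a substantial amendment. The Safety correction does not touch the primary analysis and need not wait for that answer.

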5.2. Modified Intent-to-Treat (mITT) Population

The Modified Intent-to-Treat (mITT) population will contain all patients who are in the Enrolled population, receive at least one dose of combination therapy, and have at least baseline and Week 8 assessments with primary efficacy data.

Document: \\eedc-vnasc01\Biosdata\Menarini\NebAml\ZZA67778\Biostatistics\Documentation\SAP\SAP_Menarini_MEIN21AmNe-Hyp001_Final_V1.0

Author: [name]

Version Number:

Final V1.0

Version Date:

11Nov2022

Template No.: CS_TP_BS016 Revision 7

Reference: CS_WI_BS005

Effective Date: 01Nov2021

5.3. Safety (SAF) Population

The Safety population will contain all patients who are in the Enrolled population and receive at least one dose of study medication (i.e., monotherapy and/or combination therapy).

5.4. Per-Protocol (PP) Population

The Per-Protocol (PP) population will contain all patients included in the Safety population who do not have any major protocol deviations that could affect the primary efficacy analyses and have at least baseline (Week 0) and Week 8 assessments with primary efficacy data.

6. GENERAL CONSIDERATIONS

6.1. Reference Start Date and Study Day

Study Day will be calculated from the reference start date and will be used to show start/stop day of assessments and events. It will appear in every listing where an assessment date or event date appears.

Reference start date is defined as the day of the first dose of study (combination therapy) (Visit 2), (Day 1 is the day of the first dose of study drug).

- If the date of the event is on or after the reference date, then:
 - Study Day = (date of event – reference date) + 1.
- If the date of the event is prior to the reference date, then:
 - Study Day = (date of event – reference date).

In the situation where the event date is partial or missing, Study Day, and any corresponding durations will appear partial or missing in the listings.

6.2. Baseline

Unless otherwise specified, baseline is defined as the last non-missing measurement taken same day or prior to reference start date (including unscheduled assessments) before first dose of study medication (i.e., combination therapy). Adverse Events (AEs) and medications commencing on

Document: \\weedc-vnasc01\Biosdata\Menarini\NebAm\ZZA67778\Biostatistics\Documentation\SAP\SAP_Menarini_MEIN21AmNe-Hyp001_Final_V1.0

Author: [name]

Version Number:

Final V1.0

Version Date:

11Nov2022

Template No.: CS_TP_BS016 Revision 7

Reference: CS_WI_BS005

Effective Date: 01Nov2021

the reference start date/time will be considered post-baseline, unless the start time of the AE is known to be prior to the first dosing of the study drug. Since there is no Lab assessment in Visit 2, Lab values collected at Visit 1 will be considered baseline for Lab data.

For combination therapy related analysis, the baseline will be the measurements that are taken at Visit 2 (Week 0). For safety analysis, if the measurement at visit 2 is missing or not collected, then visit 1 data will be considered.

6.3. Retests, Unscheduled Visits and Early Termination Data

In general, for by-visit summaries, data recorded at the nominal visit will be presented. Unscheduled measurements will not be included in by-visit summaries. Listings will include scheduled, unscheduled, retest and early discontinuation data.

6.4. Windowing Conventions

No visit window conventions are applicable for this study.

6.5. Statistical Tests

The default significant level will be (5%); confidence intervals will be 95% and all tests will be two-sided, unless otherwise specified in the description of the analyses.

6.6. Common Calculations

For quantitative measurements, change from baseline will be calculated as:

- Test Value at Visit X – Baseline Value

And for change between Visit 3 and Visit 4 will be calculated as:

- Test Value at Visit 4 – Visit 3 Value

6.7. Software Version

All analyses will be conducted using SAS Enterprise Guide version 8.2.

Document:	\\veedc-vnasc01\Biosdata\Menarini\NebAml\ZZA67778\Biostatistics\Documentation\SAP\SAP_Menarini_MEIN21AmNe-Hyp001_Final_V1.0		
Author:	[name]	Version Number:	Final V1.0
		Version Date:	11Nov2022
Template No.:	CS_TP_BS016 Revision 7	Reference:	CS_WI_BS005
Effective Date:	01Nov2021		

7. STATISTICAL CONSIDERATIONS

Summaries will include descriptive statistics for continuous variables (sample size [n], mean, standard deviation [SD], median, minimum and maximum) and for categorical variables (frequency [n] and percentage), unless otherwise stated in the relevant section. Percentages will be based on the number of patients within the relevant analysis population and treatment arm, or the number of patients with data available where relevant.

If the original data has N decimal places, then the summary statistics will have the following decimal places:

Minimum and maximum: N

Mean, median, Q1, Q3, confidence intervals, ratios: N + 1

SD: N + 2

Percentages will be reported to one decimal place. P-values should be reported to three decimal places, except values <1.000 but >0.999 will be presented as '>0.999' (e.g., 0.9998 is presented as >0.999); and values <0.001 will be presented as '<0.001' (e.g., 0.0009 is presented as <0.001)

7.1. Adjustments for Covariates and Factors to be Included in Analyses

The following covariates/factors are used in the analyses.

- Treatment
- Age
- Gender
- Body Mass Index
- Baseline DBP

7.2. Multicenter Studies

This study will be conducted by multiple investigators at multiple centers internationally. Center pooling will not be carried out for use in analyses for this study.

7.3. Missing Data

All analyses will be performed on observed data. Missing data will not be imputed for this study.

Document: \\eedc-vnasc01\Biosdata\Menarini\NebAml\ZZA67778\Biostatistics\Documentation\SAP\SAP_Menarini_MEIN21AmNe-Hyp001_Final_V1.0

Author: [name]

Version Number:

Final V1.0

Version Date:

11Nov2022

Template No.: CS_TP_BS016 Revision 7

Reference: CS_WI_BS005

Effective Date: 01Nov2021

Copyright © 2009, 2010, 2012, 2016, 2018, 2019, 2021 IQVIA. All rights reserved. The contents of this document are confidential and proprietary to IQVIA Holdings Inc. and its subsidiaries. Unauthorized use, disclosure or reproduction is strictly prohibited.

7.4. Multiple Comparisons/ Multiplicity

Not Applicable

7.5. Examination of Subgroups

Subgroup analyses will be conducted as stated in the exploratory analysis sections. It should be noted that the study was not designed to detect treatment differences with high statistical power within subgroups.

The following subgroups will be assessed and described within the exploratory analysis sections on ENR and mITT populations respectively.

- Hypertension grade at screening
- Presence of diabetes (patients with or without diabetes) at screening
- Presence of hypercholesterolemia (patients with or without hypercholesterolemia) at screening

Hypertension grade at screening is derived as follows;

- $140 \leq \text{SBP} < 160$ or $90 \leq \text{DBP} < 100$
- $160 \leq \text{SBP} < 180$ or $100 \leq \text{DBP} < 110$

Patients with presence of diabetes and hypercholesterolemia at screening will be identified from the medical history data using the preferred terms. Presence of diabetes can be identified using the preferred terms "Diabetes mellitus" Or "Type 2 diabetes mellitus" and hypercholesterolemia using "Dyslipidaemia" or "Hypercholesterolaemia" or "Hyperlipidaemia" or "Type IIa hyperlipidaemia" or "Type V hyperlipidaemia".

Patients with hypercholesterolemia at screening can be identified based on the clinical significance of the total cholesterol value collected in the blood chemistry laboratory data. If the total cholesterol at screening has clinical significance as per the investigator's input, then the patient will be considered for hypercholesterolemia and the details will be entered in the medical history data.

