### *Study Code:* MEIN/21/AmNe-Hyp/001

### 6.2.1 Inclusion Criteria

A patient will be considered eligible for inclusion in the study only if all of the following criteria are met:

- 1. Male or female patients with Grade 1 2 hypertension with mean sitting SBP ≥140 mmHg and ≤179 mmHg and/or mean sitting DBP ≥90 mmHg and ≤109 mmHg at screening (in accordance with the 2018 ESC/ESH guidelines definition), ≥18 and <65 years of age, on monotherapy treatment either with BBs or CCBs for at least 4 weeks before Visit 1 (screening).
- 2. Patients are able to understand and have freely given written informed consent at Screening Visit.
- 3. Patients who are able to comply with all study procedures and who are available for the duration of the study.
- 4. Ability to take oral medication and willing to adhere to the drug regimen.
- 5. Female patients are eligible to participate if not pregnant, or not breastfeeding and if they refrain from donating or storing eggs. For females of reproductive potential: use of highly effective contraception (eg. method of birth control throughout the study period and for 4 weeks after study completion defined as a method which results in a failure rate of <1% per year) such as:
  - Combined hormonal contraception (estrogen- and progestogen-containing) associated with inhibition of ovulation (oral, intravaginal, and transdermal).
  - Progestogen-only hormonal contraception associated with inhibition of ovulation (oral, injectable, and implantable).
  - Intrauterine device.
  - Intrauterine hormone-releasing system.
  - Bilateral tubal occlusion.
  - Vasectomized partner (procedure conducted at least 2 months before the screening), (provided the partner is the sole sexual partner of the trial patient and that the vasectomized partner has received medical assessment of the surgical success).
- 6. A male patient must agree to use contraception during the whole study period and for at least 1 week after the last dose of study treatment and refrain from donating sperms during this period.

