## **12.2 Determination of Sample Size**

Considering a screen failure and a drop-out rate of 25% from Visit 1 to Visit 4 (End of Treatment), the number of patients to be screened are 290. Two-hundred and sixteen patients with uncontrolled hypertension, are planned to be included at screening in the assessment period lasting for 8 weeks. A total sample size of 216 patients is required to achieve 90%

NENARINI	Corporate Medical De		rtment	
	P	rotocol Template		
Identification Number	Version Number	State	Effective date	
FORM-000050125	2.0, CURRENT	Effective	08 Jan, 2021	

Study Code: MEIN/21/AmNe-Hyp/001

power at 5% significance level assuming a difference in mean DBP from baseline to 8 weeks of 4 mmHg and a standard deviation (SD) for this difference of 10 mmHg. The mean change in DBP for null hypothesis is set at 2 mmHg.

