3. STUDY DESIGN

3.1. General Description

This is a Phase IV, interventional, open-label, multicenter, multinational study with 2 study periods (a run-in period of 4 weeks and an assessment period of 8 weeks). Patients with hypertension with systolic blood pressure (SBP) ranging from ≥ 140 to ≤ 179 mmHg and diastolic blood pressure (DBP) ranging from ≥ 90 to ≤ 109 mmHg on treatment with any beta-blockers (BBs) or calcium channel blockers (CCBs) including NEB 5 mg or AML 5 mg for at least one month prior to Visit 1 will be screened for eligibility. On the same day of the Screening visit, eligible patients will enter into a run-in period after screening, during which:

- Patients receiving NEB 5 mg or AML 5 mg will continue the same therapy for 4 weeks.
- Patients on any other BBs or CCBs will be switched to NEB 5 mg or AML 5 mg.

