10. DEMOGRAPHIC AND OTHER BASELINE CHARACTERISTICS

Demographic data and other baseline characteristics will be presented for the ENR population.

No statistical testing will be carried out for demographic or other baseline characteristics.

Document: \\eedc-vnasc01\Biosdata\Menarini\NebAml\ZZA67778\Biostatistics\Documentation\SAP\SAP_Menarini_MEIN21AmNe-Hyp001_Final_V1.0

Author: [name]

Version Number:

Final V1.0

Version Date:

11Nov2022

Template No.: CS_TP_BS016 Revision 7

Reference: CS_WI_BS005

Effective Date: 01Nov2021

The following demographic and other baseline characteristics will be reported for this study:

- Age (years)
- Age Category (<40 Years, ≥40 Years)
- Sex
- Childbearing potential
- Race
- Hypertensive Medication status at Screening (Visit 1)
 - NEB 5mg or AML 5 mg
 - Other BBs or CCBs
- Weight (kg)
- Height (cm)
- BMI (kg/m²)
- Presence of Type 2 diabetes mellitus at Screening (Yes/ No)
- Hypertension grade at Screening
- Presence of Hypercholesterolemia at Screening (with Hypercholesterolemia/ without Hypercholesterolemia)
- Mean sitting DBP at Screening (mmHg)
- Mean sitting SBP at Screening (mmHg)

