16.3.2. Analysis of Exploratory Efficacy Variables

Exploratory efficacy variables will be summarized in a descriptive manner using ENR and mITT populations for Visits 1, 2, 3 and 4.

- Change in sitting DBP and SBP from Visit 1 (Week -4) will be using paired t-test. The p-value obtained from the paired t-test will be presented for the visits - Visit 2 (Week 0), Visit 3 (Week 4) and Visit 4 (Week 8). Assumption of Normality will be investigated using Wilk-Shapiro test. If the data is found to be non-Normal, then paired t-test will be replaced by Wilcoxon signed rank test. A descriptive summary using n, mean, median, SD, Q1, Q3, minimum, and maximum is also presented.
- Change in mean sitting DBP and SBP for uncontrolled patients between Visit 2 (Week 0) and Visit 3 (Week 4) will be using paired t-test. The p-value obtained from the paired t-test along with n, mean, median, SD, Q1, Q3, minimum, and maximum will be presented. Assumption of Normality will be investigated using Wilk-Shapiro test. If the data is found to be non-Normal, then paired t-test will be replaced by Wilcoxon signed rank test.
- The number of patients achieving BP goal (sitting BP < 130/80 mmHg) will be summarized for Visits 2, 3, and 4, along with percentage and 95% CI for the proportion. A p-value using exact McNemar's test will be presented to compare the proportion of patients achieving the BP goal (sitting BP < 130/80 mmHg) between Visit 2 and Visit 3 as well as Visit 2 and Visit 4. A p-value using McNemar's test will be presented to compare the proportion of patients achieving the BP goal (sitting BP < 130/80 mmHg) between Visit 3 and Visit 4.
- The number of patients achieving BP goal (sitting BP < 130/80 mmHg) will be summarized for Visits 2, 3 and 4, along with percentage for each of the subgroup specified under section 7.5 of the SAP.

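### The SAP's two hypertension-grade classes overlap, so a patient whose systolic and diastolic readings fall in different bands meets both

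*SAP*

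**What the plan says.** SAP Section 7.5 introduces the variable with "Hypertension grade at screening is derived as follows" and lists two lines:

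| Line | SBP (mmHg) | | DBP (mmHg) |
|---|---|---|---|
| First (lower grade) | 140 to below 160 | or | 90 to below 100 |
| Second (higher grade) | 160 to below 180 | or | 100 to below 110 |

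The first line does not require the other component to be below the higher band. Nothing says which line is applied first.

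The variable is used twice. SAP Section 10 reports "Hypertension grade at Screening" as a baseline characteristic. SAP Section 16.3.2 summarizes patients at BP goal at Visits 2, 3 and 4 "along with percentage for each of the subgroup specified under section 7.5 of the SAP".

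Two other places bear on the point. Protocol Section 2.1 treats a patient as Grade 3 when either component alone reaches its threshold (SBP 180 or DBP 110). Protocol Section 6.2.1 ties Grade 1–2 to a named guideline but does not write out how discordant readings are graded.

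**The concern.** A subgroup variable should place each patient in exactly one class. Here, any patient with one component in the lower band and the other in the higher band meets both definitions. The same text then supports at least three programs:

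- **Two flags:** discordant patients are counted in both grades. The subgroup denominators add up to more than the population, and the two baseline percentages can sum above 100%.
- **Listed order, first match wins:** every discordant patient is filed in the lower grade. That runs against the Grade 3 logic in Protocol Section 2.1, where one high component is enough.
- **Reverse order:** every discordant patient is filed in the higher grade, which is probably what was meant.

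The choice would be left to the programmer, in an open-label study. Under the first two options the comparison of BP control between grades is blurred.

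**Working it through.** The documents state no figure for the overlap, so there is none to reproduce.

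**Step 1: logic.** Take every whole-number pair with SBP 140–179 and DBP 90–109. That is 40 × 20 = 800 pairs. Discordant pairs are (SBP 140–159 with DBP 100–109) plus (SBP 160–179 with DBP 90–99), which is 20 × 10 + 20 × 10 = 400. So 400/800 = 50% of pairs meet both lines, and none meets neither. This is a share of possible readings, not of patients. With one component allowed below its range, still no eligible pair is left unclassified.

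**Step 2: search for a tie-break.** None appears in Protocol Sections 5 or 6.2.1, or in SAP Sections 3.3 (changes from protocol), 7.5, 10 or 16.3.2. The reference code in SAP Appendix 1 does not derive grade.

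**Step 3: share of patients.** This needs the joint distribution of screening SBP and DBP, which neither document gives. The only spread stated is "a standard deviation (SD) for this difference of 10 mmHg" (Protocol Section 12.2), and that is for the change in DBP. It also depends on eligibility, which is worded in two ways:

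- SAP Section 3.1 describes patients in the SBP range and with "diastolic blood pressure (DBP) ranging from ≥ 90 to ≤ 109 mmHg", so both components must be in range.
- Protocol Section 6.2.1 has "mean sitting SBP ≥140 mmHg and ≤179 mmHg and/or mean sitting DBP ≥90 mmHg and ≤109 mmHg at screening", so one is enough.

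Assumed inputs: bivariate normal before truncation, SBP mean 140–160 and SD 8–15, DBP mean 86–98 and SD 6–10, correlation 0.2–0.7. That gives 960 parameter sets with 400,000 draws each, rounded to whole mmHg and cut to the eligible range, with no component at Grade 3 level.

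| Eligibility wording | Median share meeting both lines | 5th–95th percentile of sets | Extremes |
|---|---|---|---|
| and/or | 22% | 8–35% | 2–42% |
| and | 40% | 20–58% | 6–84% |

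**Step 4: what the coding does, in one assumed case.** Take SBP mean 150 (SD 12), DBP mean 94 (SD 8), correlation 0.5, and both components in range. About 49% meet the second line and 35% meet both. The share meeting the first line is (100 − 49) + 35 = 86%.

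| Coding | Grade 1 | Grade 2 | Sum |
|---|---|---|---|
| Two flags | 86% | 49% | 135% |
| Listed order | 86% | 49 − 35 = 14% | 100% |
| Higher component decides | 51% | 49% | 100% |

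In this case 35/49, or about 71%, of those meeting the higher-grade line also meet the lower one.

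**The case against.** The strongest reply is that the intent is plain. Protocol Section 2.1 lets either component place a patient in Grade 3, and inclusion criterion 1 refers to a published definition. By analogy the higher component decides, and the SAP lines merely transcribe that convention incompletely. The SAP also refers to output templates that are not among the documents and might settle the matter. This stands as evidence of what was meant. It does not rescue the text: SAP Section 7.5 presents its lines as the derivation, and taken literally they give a different result.

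The reply is also right about scale. The subgroup summary in SAP Section 16.3.2 has counts and percentages only, without a test. Section 7.5 itself warns of low power within subgroups. Grade is not among the covariates in Section 7.1 and does not enter Sections 16.1 or 16.2.

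Three stronger readings are tempting, and the documents do not support them:

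- *A fifth to a third of patients are in both grades.* That fits some assumed distributions, but the plausible span is much wider and depends on which eligibility wording applies.
- *Most Grade 2 patients would be filed as Grade 1.* This is likely but not established. Under and/or eligibility, assumed distributions put the share at about 40–80%, and it falls below half in roughly one set in six.
- *BP-goal percentages would exceed 100%.* With each subgroup as its own denominator they cannot. Only the sum across the two baseline categories can.

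**Conclusion.** The derivation in SAP Section 7.5 is wrong as written: its two classes are not mutually exclusive, and nothing in either document resolves discordant readings. This follows from the text alone and needs no assumption.

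The share of patients affected cannot be known from the documents. On the assumptions above it is roughly 8–35% with and/or eligibility and 20–58% when both components must be in range. If grades were coded as two flags, the baseline row would sum to 100% plus that share, so about 108–135% or 120–158%.

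The consequence is confined to the exploratory BP-goal summary by grade and one row of the baseline table. No primary or secondary result changes. This is a minor correction.

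**What to change.** In SAP Section 7.5, replace the two lines with one ordered rule: Grade 2 if SBP is 160 to below 180 or DBP is 100 to below 110 mmHg; otherwise Grade 1 if SBP is 140 to below 160 or DBP is 90 to below 100 mmHg. State that this one variable feeds both SAP Section 10 and Section 16.3.2. The rule follows the either-component logic of Protocol Section 2.1 and leaves no eligible patient unclassified or counted twice.

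The cost is one sentence, with no effect on data collection, sample size or the main analyses. The SAP is dated 11 November 2022, the protocol planned last patient out for the beginning of December 2022, and Protocol Section 12.7 allows the SAP to be finalized up to database lock. If tables have already been produced, the report should say how discordant patients were coded. The *and* and *and/or* eligibility wordings should be reconciled separately, because they determine how many such patients there are.
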